5.2 Statistical Analyses

Data collected in this study will be documented using summary tables. Descriptive statistics will be provided. The statistics for continuous variables will include mean, standard deviation, minimum, maximum, and sample. Categorical variables will be described with numbers and percentages. Comparisons between the groups will be presented with Differences (with 95% Confidence Intervals) and/or P-values. Percentages will be rounded to one decimal place.

Primary Objective Analyses

To evaluate the diagnostic accuracy of the "sonographic COPD score" for COPD diagnosis, we will calculate sensitivity, specificity, positive predictive value (PPV), and negative predictive value (NPV). We will then construct a Receiver Operating Characteristic (ROC) curve based on the sensitivity and specificity values to evaluate the performance of the POCUS score compared to the gold standard test, the pulmonary function test. The area under the ROC curve (AUC) will be calculated to assess the accuracy of the POCUS score in diagnosing COPD. Performances are evaluated at two different operation points: the first one is at 80% of sensitivity, and the other is at knee-point, which represents the best point reached by the ROC curve, close to the upper left bond. The presence of obstructive lung disease (OLD) detected by both ultrasound and PFTs will be labeled as true positive, the presence of OLD detected only by ultrasound and not by PFTs will be labeled as a false positive, no OLD detected by both ultrasound and PFTs will be labeled as true negative, and the presence of OLD detected by PFTs and not by ultrasound will be labeled as a false negative.

Secondary Objective Analyses

- To estimate the association between the sonographic score and the most recent (<5 years) computed tomography (CT) scan score (i.e., emphysema score) - we will use a Spearman's rank correlation coefficient.
- To estimate the association between the sonographic score and the patient's subjective severity of dyspnea (estimated by the mMRC scale)- we will use the Mann-Whitney U test to determine the association between the sonographic score and the mMRC scale.
- To estimate the association between the sonographic score and the patient's diffusion lung capacity (DLCO) - We will use the Mann-Whitney U test to determine the association between the sonographic score and DLCO.
- To determine the sonographic components that are the most sensitive for the diagnosis of OLD - we can use a logistic regression analysis. The regression will provide estimates of the effect of each sonographic component on the probability of being diagnosed with OLD. In this analysis, we can use the sonographic components as predictor variables and OLD diagnosis as the outcome variable.
- To assess the additive value of the patient's smoking status to the sonographic score's diagnostic accuracy- will be based on a logistic regression analysis. In this analysis, we can use the sonographic score and smoking status as predictor variables and OLD diagnosis as

the outcome variable. The regression will provide estimates of the effect of each predictor on the probability of being diagnosed with OLD, as well as an estimate of the additional effect of smoking status beyond the sonographic score.

All statistical tests and/or confidence intervals, as appropriate, will be performed at $\alpha=0.05$ (2-sided) or $\alpha=0.025$ (1-sided), except for those specified otherwise. All p-values reported will be rounded to three decimal places. All statistical analyses will be conducted using SPSS 29.0 statistical software (IBM Corp Armonk, NY, USA).

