STUDY PROCEDURES	We plan to conduct random POCUS scans at the respiratory institute of Soroka University Medical Center on patients who are sent for pulmonary function tests (PFTs) for any reason and provide each patient with a sonographic score, comprised of several criteria (table 1).
DATA TO CAPTURE	Aside from the sonographic data, we plan to collect descriptive data from the hospital's medical records (i.e., smoking history, comorbidities, past radiographic exams, BMI, etc.) and the PFTs results.
OUTCOMES AND ANALYSES	The diagnostic accuracy of the POCUS examination, including sensitivity, specificity, positive predictive value (PPV), and negative predictive value (NPV) of obstructive lung diseases (OLDs) will be calculated using contingency tables with PFTs findings as the gold standard.
DATA MANAGEMENT AND ANALYSIS	The study will be overseen and managed by the Soroka Clinical Research Center.

Table of Contents

Page	Content
1	Title Page
2	Investigator signature page
3	Study protocol
5	Abbreviations and Definitions
6-7	Background
8-11	Design
12	Working hypothesis and objectives
12-13	Study population
13	Enrollment and patient screening
14	Study procedure and duration
15-16	Data to capture
17-19	Statistical Considerations and Analysis Plan
20-22	Adverse events
23-24	Ethical issues and subject confidentiality
25	References
26	Supplements

Abbreviations and Definitions

Abbreviation	Term
A4C	Apical 4-chamber (view)
COPD	Chronic obstructive lung disease
DLCO	Diffusing capacity for carbon monoxide
GS	Gold standard
LV	Left ventricle
mMRC	Modified Medical Research Council (Dyspnea Scale)
OLD	Obstructive lung diseases
PFTs	Pulmonary function test(s)
POCUS	Point of care ultrasound
PLAX	Parasternal long axis (view)
SX	Subxiphoid (view)

Definitions

3 Background

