Figure 1 – The ultrasound probe is placed at zone 1 on the anterior chest.

Figure 2 – The formal 3-part cardiac exam (Parasternal long axis view (PLAX), Apical four-chambers view (A4C), and the subcostal view (sub-xiphoid, SX)

Diagnosis Considerations and Calculation

Chest scan grading

The anterior chest (Zone 1) will be examined bilaterally (see Figure 1) searching for A-lines (meaning aerated “open” alveoli) versus B-lines (which suggest alveolar flooding). A sonographic scan consistent with multiple A-Lines on both sides of the chest strengthens the diagnosis of OLD. Patients with three A-Lines or more will claim the maximal grade of 2 points on the corresponding side, meaning that a “perfect” score regarding the anterior chest is 4 (see Table 1).

Cardiac views grading

We will use three formal echocardiographic views for scoping the heart: The PLAX, A4C, and SX views (see Figure 2). Each view will provide the patient with an image quality score ranging from 0-2 depending on the quality of the view (see Table 1). The score for the different cardiac views, from “No discernable anatomy” to “Great view”, is relied on the level of detection of the left ventricular endocardial border. This criterion applies to all three cardiac views. We expect that a scan consisting of OLD will be characterized by poor PLAX and A4C views and great SX views. Therefore, maximal cardiac score (=6) will be granted to a scan consisting of a great (i.e. when the left ventricle (LV)endocardial border is clear) SX view and no discernable anatomy noticed in the PLAX and A4C views.

Grading synthesis

A sum of the cardiac and chest scans will give a final sonographic score between 0 to 10. A scan most consistent with OLD will be given a score of 10.

In the case of any abnormal finding in the chest or the cardiac POCUS, direct notification to the pulmonologist and the primary caregiver will be given by the research team, as well as written notification in the patient's electronic medical record. The patient and the primary caregiver will be notified that this exam is not a diagnostic cardiac exam focused only on detecting the level of the endocardial imaging quality. If b lines or abnormal left ventricular function are detected, the information will be transferred to involved teams.

Table 1

The Sonographic Score Components for the Diagnosis of OLD

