4.1 Working Hypothesis

We hypothesize that a high sonographic score (8-10 points) will have at least an equal diagnostic accuracy compared to the reference diagnosis with PFTs.

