5.1 Sample Size Considerations

In this study, the sample size calculation was aimed to ensure an accurate estimate of sensitivity (Se) and specificity (Sp) of the POCUS examination vs the gold standard PFTs. We aim to enroll a total of 200 patients. The calculation stems from the speculation that the Se of the test will be 85%, with a confidence interval of 90% and the maximal width of the interval will be up to $\pm 7\%$.

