5.3 Primary Endpoints

Our primary endpoint is to diagnose OLD with POCUS examination (compared to the PFT which is considered the gold standard).

6 Adverse Events

There are no known adverse events to the point-of-care ultrasound exam.

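### The primary analysis gives no score that counts as a positive ultrasound: the hypothesis uses 8-10, but section 5.2 names only operating points read off the study's own ROC curve

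*Combined protocol and SAP*

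**What the plan says.** Section 4.1 states: "We hypothesize that a high sonographic score (8-10 points) will have at least an equal diagnostic accuracy". This is the only score threshold in the protocol.

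The primary analysis in section 5.2 lists sensitivity, specificity, PPV and NPV, and continues: "We will then construct a Receiver Operating Characteristic (ROC) curve based on the sensitivity and specificity values". It adds the AUC and then: "Performances are evaluated at two different operation points: the first one is at 80% of sensitivity, and the other is at knee-point". The cells of the 2x2 table are defined in words only, for example: "The presence of obstructive lung disease (OLD) detected by both ultrasound and PFTs will be labeled as true positive". No score is attached to any cell.

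Other places where a cut-off might stand do not supply one:

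- Section 4, Grading synthesis: "A scan most consistent with OLD will be given a score of 10". Table 1 gives component points only.
- Section 5.3: "Our primary endpoint is to diagnose OLD with POCUS examination".
- Section 2, Outcomes and Analyses: the four accuracy measures "will be calculated using contingency tables with PFTs findings as the gold standard".
- Section 3 mentions a presumptive diagnosis made on site from the sonographic data, without a rule for it.

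Section 5.1 sizes the study at 200 patients on an assumed sensitivity of 85%, with a 90% confidence interval of ±7%.

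**The concern.** Sensitivity, specificity, PPV and NPV each need one binary rule for a positive ultrasound. Section 5.2 can be read in two ways. On reading A, the four measures come from one table at 8-10 points and the ROC curve follows as a further analysis. On reading B, the sensitivities and specificities are those at every cut-off, since the curve is built from them, and performance is reported at the two named points. The on-site presumptive diagnosis is a third candidate for what ultrasound detected. Nothing in the documents chooses among these.

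At the first named point sensitivity is set by selection, so that point says nothing about whether the 85% in section 5.1 was right. At the second, the cut-off is tuned on the data used to report its performance. The hypothesised 8-10 rule might therefore never be reported as the primary result, and the headline cut-off could be chosen once the results are known.

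**Working it through.** **Inputs from the documents.** Score 0-10 (section 4, Grading synthesis). Hypothesised positive range 8-10 (4.1). Operating points: 80% sensitivity and the knee-point (5.2). N = 200, sensitivity 85%, 90% interval, ±7% (5.1).

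**The plan's own figure.** n = z²·Se·(1−Se)/d² = 1.645² × 0.85 × 0.15 / 0.07² = 70.4, so 71 patients with obstructive lung disease (OLD). A total of 200 follows if about 35.5% of patients have OLD (71/200). No prevalence is stated, so 200 can be neither confirmed nor refuted. The point here does not depend on it.

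**Assumptions.** No score distribution is given. All figures below take a normal score rounded to 0-10, so that Se(≥k) = 1 − Φ((k − 0.5 − mean)/SD). The 80% point is read as the highest cut-off with observed sensitivity of at least 80%.

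**Step 1. How far the candidate rules can lie apart.**

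| OLD mean / SD | Se at ≥8 | Highest cut-off with Se ≥80% |
|---|---|---|
| 6 / 1.5 | 15.9% | 5 |
| 6 / 2.0 | 22.7% | 4 |
| 7 / 1.5 | 36.9% | 6 |
| 7 / 2.0 | 40.1% | 5 |
| 8 / 1.5 | 63.1% | 7 |
| 8 / 2.0 | 59.9% | 6 |
| 9 / 1.5 | 84.1% | 8 |
| 9 / 2.0 | 77.3% | 7 |

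In seven of the eight cases the 80% point is not the hypothesised cut-off.

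**Step 2. If the 85% is meant at 8-10 (an assumption).** The mean is 7.5 + SD·Φ⁻¹(0.85), which is 9.05 for SD 1.5 and 9.57 for SD 2.0. Sensitivity at ≥9 is then 64.4% or 70.4%. In simulated samples with 50, 70 or 100 OLD patients, the 80% rule picks ≥8 in 79-94% of samples, so here it largely agrees with the hypothesis.

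The knee-point need not agree. Take the non-OLD mean lower by √2·SD·Φ⁻¹(AUC), N = 200, and the cut-off closest to the upper left corner:

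| Latent AUC | Samples picking ≥8 |
|---|---|
| 0.70 | under 1% |
| 0.80 | 6-19% |
| 0.90 | 79-97% |

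At AUC 0.80, specificity at ≥8 is Φ(√2·Φ⁻¹(0.80) − Φ⁻¹(0.85)) = Φ(1.190 − 1.036) = 56%. The knee-point reports on average 68-72% sensitivity and 73-76% specificity, against 85% and 56% at ≥8.

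**Step 3. If the 85% is wrong at 8-10.** With true sensitivity 63.1% or 59.9% (mean 8 in Step 1) and 50-100 OLD patients, the binomial probability that a table at ≥8 shows sensitivity below 80% is over 99%. The 80% point can never show it, by construction.

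**Step 4. Optimism from tuning on the same data.** With the closest-to-corner rule, apparent minus true performance averages 0 to 1.6 points in sensitivity and 0.1 to 2.1 points in Se+Sp. With maximum Youden it is about 1 to 4 points in Se+Sp in the Step 2 settings.

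**The case against.** The strongest reply is that a link is missing, not a threshold. The 8-10 range is in the protocol, no competing score appears, section 5.2 puts the four measures before the ROC curve, and the summary speaks of contingency tables without mentioning operating points. Reading A is the more natural one. That stands, but it supports the fix: if ≥8 was always meant, section 5.2 should say so and not name two other points alone.

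Second, the on-site diagnosis could be the ultrasound result. The operator is blinded to PFT results (4.6), so that call would be fixed before linkage and could not be tuned. This is a fair third reading, but the call has no stated rule and is not mentioned in 5.2.

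Third, the 85% is a planning assumption for precision, and reporting specificity near a fixed sensitivity is ordinary practice. That also stands: the 80% point is a legitimate supporting result, but it cannot be the estimate of sensitivity for which the study was sized. Step 3 also depends on reading that point as at least 80%, since section 5.2 gives no rule for an integer score.

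Fourth, the percentages rest on assumed distributions and on the knee criterion. Under maximum Youden the knee-point picks ≥8 in 11-18% of samples at AUC 0.70 and 23-34% at 0.80. Section 5.2's description of the knee fits closest-to-corner better, but it names no formal criterion. The figures illustrate; they do not forecast.

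**Conclusion.** The concern holds. No section attaches a score to a positive ultrasound in the primary 2x2 table, the 8-10 range never reaches section 5.2, and both operating points named there are taken from the study's own ROC curve. This follows from the text and needs no simulation.

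The practical size depends on the unknown score distribution. If sensitivity at ≥8 is about 85% and the AUC is near 0.90, the rules mostly agree. At lower AUC, or if sensitivity at ≥8 is well below 85%, they describe materially different tests. Knee-point optimism is minor by comparison.

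The AUC needs no cut-off and is unaffected. Scores are recorded at every level, so sensitivity and specificity at ≥8 can always be computed; what is missing is the stated rule and its designation as primary. This should be fixed, but it does not invalidate the design.

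**What to change.** In section 5.2:

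- Define a positive test for the primary 2x2 table as a score of 8 or more, matching 4.1. Report sensitivity, specificity, PPV and NPV at that cut-off as the primary result, with confidence intervals at a stated level (5.1 plans with 90%, while 5.2 sets a two-sided α of 0.05).
- Keep the AUC and both ROC operating points as supporting results. Report the two points at observed integer cut-offs under a stated rule, for example the highest cut-off with sensitivity of at least 80%, and the cut-off closest to the upper left corner. Label them as data-derived.
- State whether the on-site presumptive diagnosis in section 3 is the same as the score rule. If it is a separate judgement, say how it will be used.

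Settle this before scores are linked to PFT results. The cost is a few sentences, with no new data and no extra patients. The downside is that sensitivity or specificity at ≥8 may look less favourable than at a cut-off picked from the data.

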4.6 Study Procedures

The study will be performed in a fully paired fashion, i.e., a direct comparison in which all study participants receive the index test (sonographic assessment) and the reference standard (PFTs).

This should enhance the resulting precision relative to the number of study participants. The three following steps are planned to take place at the same visit:

1. Enrollment, including obtaining written informed consent.
2. PFTs, performed as planned.
3. A sonographic evaluation comprised of both lung and cardiac POCUS scans, performed by an experienced sonographer, blinded to the patient's medical history or PFTs results.

Steps two and three can be replaced in order as long as the POCUS operator is blinded to the PFTs results. The PFT technician is not part of the study team and will be blinded to the POCUS findings as well.

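### The Mann-Whitney U test is assigned to the score's association with mMRC and with DLCO, but no grouping variable or cut is given

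*Combined protocol and SAP*

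**What the plan says.** Section 4.2.2 lists five secondary objectives. Three ask for an estimate of the association of the sonographic score with another measure: the CT emphysema score, mMRC dyspnoea and DLCO. Section 5.2 gives a method for each:

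- CT emphysema score: "we will use a Spearman's rank correlation coefficient".
- mMRC: "we will use the Mann-Whitney U test to determine the association between the sonographic score and the mMRC scale".
- DLCO: "We will use the Mann-Whitney U test to determine the association between the sonographic score and DLCO".

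Nothing further is said about the last two. The general paragraph of Section 5.2 adds "Comparisons between the groups will be presented with Differences (with 95% Confidence Intervals) and/or P-values" without saying which groups are meant.

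Score cuts appear in two places. Section 4.1 hypothesises that "a high sonographic score (8-10 points) will have at least an equal diagnostic accuracy" relative to PFTs. The primary analysis in Section 5.2 evaluates two operating points: "the first one is at 80% of sensitivity, and the other is at knee-point". Both statements concern diagnostic accuracy.

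**The concern.** A Mann-Whitney test needs one two-level variable and one ordinal or continuous variable. Neither pair named in Section 5.2 supplies the two-level variable, so the analyst must create it. The options include the score at 8, the score at an ROC-derived point, mMRC at any of four cuts, or DLCO at any value. They give different p-values and answer different questions.

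Two things are at stake. If the choice is left until the data are in, the reported result can depend on it. And even a split fixed in advance gives a single contrast. It discards information and does not describe how strongly the two measures move together across their range, which is the natural reading of an objective to estimate association.

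**Working it through.** The plan gives no figure for these two analyses, so there is none to reproduce. The core of the point is a comparison of sections; the simulation only shows the size of the consequences.

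**1. Scale of each variable.** The score is a sum from 0 to 10 (Section 4, grading synthesis). mMRC has grades 0-4 in Section 10 and is coded 1-4 in Section 4.8.1; on either version it has more than two levels. DLCO is a measured diffusing capacity with no category or threshold in any section, and is taken here as continuous.

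**2. Search for a grouping.**

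- The 8-10 band (Section 4.1) and the two ROC operating points (Section 5.2) serve diagnostic accuracy and are not linked to mMRC or DLCO.
- The general sentence on group comparisons defines no groups, and Section 4.6 describes one fully paired cohort.
- Grouping by PFT-defined OLD does not work: comparing the score by OLD status leaves out mMRC or DLCO, and comparing mMRC or DLCO by OLD status leaves out the score.

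**3. Possible size of the 8-10 group.** Suppose the 85% sensitivity in Section 5.1 applied to this band (the plan ties it to no cut). Then share = prevalence × 0.85 + (1 − prevalence) × (1 − specificity). With assumed prevalence 25-50% and specificity 70-95%:

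- lowest: 0.25 × 0.85 + 0.75 × 0.05 = 25.0%
- highest: 0.50 × 0.85 + 0.50 × 0.30 = 57.5%

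**4. Power.** From the plan: N = 200 and two-sided 0.05. Assumed: bivariate normal data; score a rounded normal (SD 2.3 points) placed so that 25-58% score 8-10; three sets of mMRC frequencies, with 5-15% in grade 4 and 35-50% in the upper group when cut at grade 2 or above. There were 5,000-10,000 replicates per setting. Spearman used the t approximation and Mann-Whitney the tie-corrected normal approximation.

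| Analysis | Correlation 0.2 | Correlation 0.3 |
|---|---|---|
| Spearman, no split | 71-78% | 97-98% |
| Mann-Whitney, near-balanced split (43-58% scoring 8-10, mMRC ≥2, or DLCO median) | 55-61% | 89-92% |
| Mann-Whitney, 25% scoring 8-10 | 49-54% | 84-88% |
| Mann-Whitney, mMRC cut at grade 4 | 23-43% | 44-78% |

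At correlation 0.4, near-balanced splits reach 99% against 100%. A second simulation (score mean 5.5, SD 2.2; mMRC 20/30/25/17/8%; 4,000 replicates) agrees. At correlation 0.2 Spearman had 75-78%, and Mann-Whitney ran from 47% (score split at 8, against mMRC) to 61% (mMRC ≥2 or DLCO median).

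**5. Type I error (correlation 0).** Each fixed split gave 4.4-5.5%. Taking the smallest p-value over four mMRC cuts gave 15.7-16.6%, and over four DLCO cuts (20th, 35th, 50th and 65th percentiles) 13.9-14.2%.

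**6. What Spearman would deliver.** Using Fisher's z with variance (1 + r²/2)/(N − 3), at r = 0.3 and N = 200:

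- z = 0.3095
- SE = √(1.045/197) = 0.0728
- limits on the z scale: 0.3095 ± 1.96 × 0.0728 = 0.167 to 0.452
- back-transformed 95% CI: 0.165 to 0.424, a half-width of about 0.13

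**The case against.** The strongest reply is that the plan already treats ultrasound as positive or negative when it defines true and false positives, and that 8-10 is the one band fixed in advance. Comparing mMRC or DLCO between high and lower scorers is then a natural reading, it is a valid use of Mann-Whitney, and a difference would be evidence of association. On that view the only necessary change is to name the grouping. This stands in part: a prespecified 8-10 split would be a legitimate analysis. But the plan does not state it, and the two ROC operating points compete with it. It would also show that an association exists without giving its strength across the scale. Nothing explains why the like-worded CT objective gets a different method.

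Several limits on the magnitude also stand:

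- Correlations, mMRC frequencies, prevalence and specificity are all assumed.
- No section suggests a cut at grade 4.
- If mMRC is coded 1-4, only three cuts exist, and the best-of-cuts error is about 12.5-13%.
- mMRC comes from medical records, so 200 is an upper bound on the number analysed.
- No secondary objective has a power target, so the power loss breaches no stated aim.

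Finally, DLCO is not itemised in Section 4.8.1 and its form is not given. Changing the test does not settle that.

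**Conclusion.** The concern holds. For two of five secondary objectives, the named test cannot be run until someone chooses a variable and a cut that the plan does not give. This conclusion needs no assumed number.

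The consequences are moderate. At a correlation of 0.2, a near-balanced split would cost roughly 15-20 percentage points of power against Spearman. The cost is larger for uneven splits and almost nil at 0.4. Type I error stays near 5% for one fixed split. It reaches 16-17% only if the most favourable of four mMRC cuts is picked on the data, which is an upper illustration and not something the documents say will be done. The power figures rest on the assumed distributions above.

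The primary sensitivity and specificity analysis is untouched. The point should be fixed before analysis but does not threaten the study's main result.

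**What to change.** In Section 5.2, replace Mann-Whitney U in the mMRC and DLCO bullets with Spearman's rank correlation and a 95% confidence interval, the coefficient already planned for the CT score. If a two-group comparison is wanted as well, name in advance the variable that is split and the cut. State the form of DLCO used (measured or percent predicted) in the same edit.

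A minor, separate point: add a code for grade 0 to the mMRC item in Section 4.8.1 so that it matches the scale in Section 10 and grade 0 patients are not lost or merged.

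The cost is a short edit to two bullets and one code. An eCRF change is needed only if grade 0 is missing there, and under Section 4.8.2 the research centre must judge it necessary. No extra patients, visits or data are required.

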4.2.2 Secondary Objective

- To estimate the association between the sonographic score and the most recent (<5 years) computed tomography (CT) scan score (i.e., emphysema score).
- To estimate the association between the sonographic score and the patient's subjective severity of dyspnea (estimated by the mMRC scale).
- To estimate the association between the sonographic score and the patient's diffusion lung capacity (DLCO).
- To determine the sonographic components that are the most sensitive for the diagnosis of COPD.
- To assess the additive value of the patient's smoking status to the diagnostic accuracy of the sonographic score.

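### The secondary objective on the most sensitive components is given only a logistic regression, which does not estimate sensitivity and could rank the five components differently

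*Combined protocol and SAP*

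**What the plan says.** Section 4.2.2 lists the objective: "To determine the sonographic components that are the most sensitive for the diagnosis of COPD". Section 5.2 repeats it for OLD (the protocol treats COPD and OLD as interchangeable) and attaches a method: "To determine the sonographic components that are the most sensitive for the diagnosis of OLD - we can use a logistic regression analysis". It then describes the result: "The regression will provide estimates of the effect of each sonographic component on the probability of being diagnosed with OLD". On the model it says only that "we can use the sonographic components as predictor variables and OLD diagnosis as the outcome variable". It does not say whether the five components enter together or one at a time, or whether the grades are treated as scores or categories.

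Elsewhere, sensitivity, specificity and predictive values are planned for the sonographic score or the ultrasound examination as a whole (Protocol Summary; Section 4.2.1; Section 5.2, Primary Objective Analyses). The general text of Section 5.2 adds that "Categorical variables will be described with numbers and percentages" and that "Comparisons between the groups will be presented with Differences (with 95% Confidence Intervals) and/or P-values". The groups are not defined there, and these tables are not linked to the component objective.

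Each Table 1 component is graded 0, 1 or 2. For the chest scan, for example, "Patients with three A-Lines or more will claim the maximal grade of 2 points on the corresponding side". The only range of values put forward as indicating OLD is 8 to 10 on the total score (Section 4.1). No cut-off is given for a single component.

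**The concern.** Sensitivity is the proportion of OLD patients in whom a component is positive. A logistic regression with OLD as outcome estimates how the odds of OLD change with the component, and that depends just as much on how often the component is positive in patients without OLD. In a joint model, each coefficient is also conditional on the other components. Two components that carry the same information, as right and left A-lines may, share their effect and each looks weaker.

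Followed as written, the plan could name a specific but insensitive component as the most sensitive, or pass over a sensitive one because its two sides overlap. The Background envisages using the scan to find OLD early where full PFTs are not accessible. A wrong statement about which view is most sensitive would mislead in that setting, because an insensitive sign misses patients.

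**Working it through.** The plan states no figure for this objective, so there is none to reproduce. Every rate below is an illustrative assumption. From the documents come only the five components graded 0–2 (Table 1), the total of 200 patients (Section 5.1) and the form of the model (Section 5.2).

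**1. Specificity.** For a yes/no component entered alone, OR = [Se/(1−Se)] × [Sp/(1−Sp)].

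- Component A, Se 0.90, Sp 0.40: (0.90/0.10) × (0.40/0.60) = 6.0.
- Component B, Se 0.45, Sp 0.95: (0.45/0.55) × (0.95/0.05) = 15.5.

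B is half as sensitive and ranks first. B draws level when Sp/(1−Sp) equals A's OR divided by 0.818 (that is, by 0.45/0.55):

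| Sp of A | OR of A | Sp at which B overtakes |
|---|---|---|
| 0.40 | 6.0 | 0.88 |
| 0.60 | 13.5 | 0.94 |
| 0.80 | 36.0 | 0.98 |

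With Sp 0.80 for both, the ORs are 9 × 4 = 36.0 and 0.818 × 4 = 3.3, and the rankings agree.

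A milder five-component example, with components independent within the OLD and non-OLD groups, so that joint and separate ORs coincide:

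| Se | Sp | OR |
|---|---|---|
| 0.80 | 0.60 | 4.00 × 1.50 = 6.0 |
| 0.78 | 0.60 | 3.55 × 1.50 = 5.3 |
| 0.70 | 0.65 | 2.33 × 1.86 = 4.3 |
| 0.65 | 0.75 | 1.86 × 3.00 = 5.6 |
| 0.60 | 0.85 | 1.50 × 5.67 = 8.5 |

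The least sensitive component has the largest OR.

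**2. Overlap, if components are entered jointly.** Take right and left A-lines with Se 0.85 each and one cardiac view with Se 0.75, all with Sp 0.80. The A-lines have correlation φ within OLD and within non-OLD; the view is independent of them within each group. Large-sample main-effects logistic fits at OLD prevalence 0.20, 0.35 and 0.50 give these adjusted ORs:

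| φ | Each A-line side | Cardiac view |
|---|---|---|
| 0 | 22.7 | 12.0 |
| 0.3 | 10.0–10.1 | 11.9–12.0 |
| 0.6 | 6.6–6.7 | 11.9–12.0 |
| 0.9 | about 5.1 | 12.0 |

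The sensitivities are the same in every row, yet the order has reversed by φ = 0.3.

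**3. Cut-off.** Suppose one component is at grade 1 or above in 95% of OLD patients and at grade 2 in 40%, and another is at 80% and 60%. The first is more sensitive at grade ≥1 (95% v 80%) and less sensitive at grade 2 (40% v 60%). Without a named cut-off the objective has no single answer.

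**4. Precision of direct estimates.** With 40 to 120 OLD patients among the 200 (assumed range), the Wilson 95% intervals are:

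| Se | 40 OLD patients | 120 OLD patients |
|---|---|---|
| 0.90 | 36/40: 0.77–0.96 | 108/120: 0.83–0.94 |
| 0.45 | 18/40: 0.31–0.60 | 54/120: 0.36–0.54 |

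These are wide at the lower end but usable for a secondary objective.

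**The case against.** The best defence is that sensitive is used loosely here for the components that contribute most to diagnosis. The sentence after the method describes exactly that, and on this reading one word is wrong and the analysis is right. The reading is possible, but the documents do not adopt it, and Sections 4.2.1, 5.1 and 5.2 use sensitivity in its technical sense. If it is what was meant, rewording settles the matter.

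Second, the method is worded permissively, and the general summary tables could show component grades in OLD and non-OLD patients. The percentage of OLD patients at or above each grade would then be the sensitivity. This is fair, and it means most of the needed table may be produced anyway. But the groups are undefined, no cut-off is named, and nothing ties those tables to this objective.

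Third, the overlap example depends on its set-up. The protocol expects parasternal and apical views to be poor together. If two cardiac views (Se 0.75, Sp 0.80) are correlated to the same degree as the A-lines, the adjusted ORs at prevalence 0.35 are 10.0 v 6.4 at φ = 0.3 and 6.65 v 4.57 at φ = 0.6, with no reversal. In the single-view set-up there is also no reversal at φ = 0.2 (12.2 v 11.9). This stands: overlap can change the order but need not. The specificity argument does not depend on it.

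Fourth, 0.40 against 0.95 is a wide contrast in specificity, and the ORs are for yes/no components while the grades run 0–2. The size of the effect in this trial is indeed unknown, although the milder example shows that extreme values are not required. Lastly, the regression itself needs no cut-off; the missing cut-off matters because the objective asks for sensitivity.

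**Conclusion.** The concern holds. The only method tied to this objective yields a quantity other than the one the objective names, and no other planned analysis is linked to it. The ranking by regression can differ from the ranking by sensitivity: in the main example a component with half the sensitivity has an OR of 15.5 against 6.0. Whether this happens here depends on component specificities and correlations that the documents do not give. If specificities are similar and components do not overlap, the rankings agree and nothing is lost. The consequence is confined to one secondary objective; the primary accuracy analysis and the sample size are unaffected.

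**What to change.** In Section 5.2, for each of the five Table 1 components, plan sensitivity and specificity against PFTs with 95% confidence intervals, at grade ≥1 and at grade 2. Name one cut-off in advance as the main one. Base the statement about the most sensitive component on these estimates, compare sensitivities as paired data within OLD patients (every participant has all five readings), and show specificity alongside. Keep the logistic regression as a supplement on independent contribution, commit to it, and state whether components enter jointly or singly.

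Alternatively, if the most informative components were intended, reword the objective in Sections 4.2.2 and 5.2 and keep the regression as the main method.

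The first option costs one table from data already to be collected and a sentence naming the cut-off. The second costs a wording change in two places.
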